2.19 Pharmacokinetics

In this study, no PK analysis will be done.

2.20 Statistical Considerations

2.20.1 *Statistical Hypotheses / Sample Size Determination*

This study is designed to evaluate the superiority of two doses of OTT166 (5 mg/day and 10 mg/day) compared to vehicle control for the treatment of DR. For each dose within each endpoint, the null hypothesis is that there is no difference between OTT166 and vehicle control or the difference is in the direction of inferiority of OTT166, and the alternative hypothesis is that there is a difference between OTT166 and vehicle control in the direction of superiority of OTT166. The vehicle control groups will be combined for all statistical analyses. No multiplicity adjustment is planned for this study.

The study will enroll approximately 210 participants randomized as described in [Section 2.14.3](#), 70 participants per group into each treatment arm and 35 participants per group into each matching vehicle control group and allowing for around 5% study attrition, aiming for at least 66 participants per treatment group and combined vehicle control group.

For the primary endpoint of improvement by at least 2 steps from BL on the DRSS at Week 24, completing 66 participants per group (active treatment BID, active treatment QID, combined vehicle control) through Week 24 will yield at least 90% power to demonstrate that the active treatment is superior to vehicle control using a 1-sided alpha of 0.05, provided that the true treatment effect (active treatment efficacy rate minus vehicle control efficacy rate) is at least 0.20 and the vehicle control efficacy rate is at most 0.06.

The sample size calculation was computed in nQuery 8.7 using a Chi square test for two proportions (continuity corrected).

2.20.2 *Outcome Measures*

The primary safety outcome measure of the study will be the proportion of participants who develop TEAEs through Week 24.

The primary efficacy outcome measure of the study will be the proportion of participants who have improved by ≥ 2 steps from baseline at Week 24 as determined by central reading center assessment using DRSS.

The secondary outcome measures are as follows:

- Proportion of participants developing worse than mild PDR (DRSS 65 and above) at Week 24
- Proportion of participants who develop ASNV at Week 24
- Time to development of PDR worse than mild (DRSS 65 and above)
- Proportion of participants who develop CI-DME at Week 24
- Time to development of CI-DME

- Proportion of participants developing VTC at Week 24
- Time to development of PDR worse than mild (DRSS 65 and above) or CI-DME
- Proportion of participants with change in DRSS steps at Week 24 compared to baseline
 - Change in DRSS steps is defined as DR worsening or improving by 1, 2, or ≥ 3 steps
- Proportion of participants with mild PDR (DRSS score 61B) at baseline who regress to NPDR (DRSS score ≤ 53) by Week 24
- Mean and median change in BCVA (ETDRS letters) from baseline to Week 24
- Lines gained/lost in BCVA ($\pm 5, 10, \text{ and } 15$ ETDRS letters) at Week 24
- Mean and median change in AUC for change in BCVA from baseline to Week 24
- Mean and median change in CST from baseline to Week 24
- AUC for change in CST from baseline to 24 weeks
- Proportion of participants who met the objective rescue criteria as defined in [Section 2.14.9](#).
- Time to meet objective rescue therapy criteria as defined in [Section 2.14.9](#).
- Time to administration of rescue therapy.

Exploratory outcomes measures will include:

- Change in Macular Volume (MV) from baseline to Week 24 for 1, 3, and 6 mm regions
 - MV will be defined as the sum of the 9 subfield measurements as provided by the imaging center
- Change in area of retinal non-perfusion from baseline to Week 24 seen on widefield fluorescein angiography (FA)
- Proportion of participants with intact foveal avascular zone (FAZ) seen on widefield FA at Week 24
- Optical coherence tomography angiography (OCTA) endpoints within the 6 mm area:
 - Change from baseline to Week 24 in FAZ area
 - Change from baseline to Week 24 in non-perfusion area
 - Change from baseline to Week 24 in vessel caliber
 - Change from baseline in ischemic Index at Week 24 defined as total area of non-perfusion divided by total area of retina visualized (28.3 mm^2)
 - Proportion of participants with new neovascularization at Week 24

- Proportion of participants with new IRMA at Week 24
- Change in vessel density from baseline to Week 24 in the superficial and deep layers

2.20.3 *Analysis Sets*

For purposes of analysis, the following analysis sets are defined:

Table 2 Analysis Sets

Analysis Set	Description
Enrolled Set (ES)	All participants who signed informed consent.
Intent-to-Treat (ITT) Analysis Set	All randomized participants who received at least one dose of study drug. Participants will be included into the analysis as randomized. This corresponds to what is referred to in ICH E9 as the Full Analysis Set.
Per-Protocol Set (PPS)	All ITT participants without any major protocol deviations that could impact the primary endpoint.
Safety Analysis Set (SS)	All participants who receive at least one dose of study drug. Participants will be included into the analysis based on treatment actually received, regardless of the treatment randomized.

The ITT Analysis Set will be used for all efficacy and BL analyses except participant disposition which will be shown for the ITT Analysis Set and for the Safety Analysis Set if the two analysis sets differ. All randomized participants are expected to be dosed and any exceptions will be described in the CSR. The PP set will be determined prior to database lock and will be used as supplementary analyses of the primary endpoint. All safety analyses will be based on the Safety Analysis Set (SS).

2.21 *Statistical Analyses*

2.21.1 *General Considerations*

Statistical analyses will include tabulations of summary data, inferential analyses, by participant listings, and figures.

All statistical tests will be one-sided and will be performed at the 5% level of significance, unless otherwise stated. The vehicle control group will be combined for all efficacy analyses, and two-sided 90% confidence intervals will be presented. Frequency counts (n and percentages) will be made for each qualitative variable. Descriptive statistics (n, mean, standard deviation [SD], median, minimum, and maximum) will be calculated for each quantitative variable, unless otherwise stated. All data will be summarized by treatment group. All safety summaries and analyses will be based upon the Safety Analysis Set by treatment group (i.e., vehicle control doses (5% BID, 5% QID), vehicle control combined, active OTT166 doses (5% BID, 5% QID), and OTT166 combined).

The BL value for analysis and reporting will be based on the last (non-missing) measurement before dosing on Day 1. If any safety measurements are repeated after dosing on Day 1, then the last (non-missing) value of any repeated measurements will be used in the descriptive statistics and in the calculation of changes from BL.

2.21.2 Efficacy Analyses

2.21.2.1 Analysis of the Primary Endpoint

The primary estimand for the primary endpoint analysis is as follows:

	Primary Estimand
Treatment conditions of interest	OTT166 5 mg/day, OTT166 10 mg/day and matching vehicle control
Participant Population	DR participants with Type 1 or Type 2 diabetes under adequate control (HbA1c \leq 12.0%) who show typical fundus alterations and have been diagnosed with moderately severe to severe NPDR or mild PDR as defined by the DRSS Steps 47, 53, and 61B, with BCVA \geq 69 ETDRS letters, CST of \leq 325 μ m, and a normal foveal contour.
Endpoint	\geq 2 steps improvement from BL in DRSS score at Week 24.
Population level summary	Difference in proportion of participants achieving \geq 2 steps improvement from BL in DRSS score at Week 24 between each OTT166 treatment group and the combined vehicle control group.
Intercurrent events (ICEs) and strategies to handle ICEs	
a. Rescue treatment due to worsening DRSS level to 65 or higher prior to assessment of DRSS at Week 24
 
Composite strategy (non-response)
 
Death prior to DRSS assessment at Week 24
 
Hypothetical strategy
 
Use of rescue treatment for any other reason prior to DRSS assessment at Week 24
 
Composite strategy (non-response)
 
Premature discontinuation of study drug for any reason prior to DRSS assessment at Week 24
 
Hypothetical strategy
 
Study drug compliance $<$ 75% through Week 24
 
Treatment policy strategy
 
b. Study drug compliance between 75% to $<$ 90% through Week 24
 
Treatment policy strategy

	ICE(s) with a composite variable strategy take priority over ICEs with other strategies. And ICEs with a hypothetical strategy take priority over ICEs with treatment policy strategy.

Handling of missing DRSS response data at Week 24 in participants without ICEs:

- multiple imputation assuming missing at random (MAR)

Handling of DRSS response data at Week 24 missing after ICEs:

- single imputation (non-response) when applying composite variable strategy
- multiple imputation assuming MAR when applying hypothetical and treatment policy strategy

Handling of DRSS response data at Week 24 observed after ICEs:

- replaced by non-response (single imputation) in the analysis when applying composite variable strategy
- replaced by multiple imputation algorithm based on data from participants not affected by the respective ICE when applying hypothetical strategy
- kept in the analysis when applying treatment policy strategy

Comparison of the primary endpoint will be made between each dose group and the combined vehicle control group using a Mantel-Haenszel (MH) test of the difference in 2 proportions stratified by the randomization stratification factor (BL DRSS score 47 or 53 or 61B). The estimated MH risk difference will be summarized along with the 2-sided 90% CI using MH stratum weights and the Sato variance estimator. The primary efficacy analysis will be performed on the ITT Analysis Set, while the PP set will be used as supplementary analyses. ICEs and missing data will be handled as described above.

The primary efficacy analysis will also be performed by demographic subgroups including age, gender, and race to assess the consistency of the treatment effect. Additional subgroup analyses may also be conducted and will be described in the Statistical Analysis Plan (SAP).

2.21.2.2 Analyses of Secondary and Other Efficacy Endpoints

Estimands for the secondary endpoint analyses will be described in the SAP.

The secondary endpoints involving proportions of participants will be analyzed using the same approach (MH test) as described for the primary efficacy analysis and based on the ITT.

Time to event secondary endpoints will be analyzed using a stratified log-rank test adjusting for the randomization stratification factor.

Continuous secondary endpoints involving change from BL will be analyzed using an analysis of covariance (ANCOVA) model with BL measurement of the variable as a covariate and treatment group and the randomization stratification factor as fixed factors. The pair-wise comparisons of each OTT166 dose group versus combined vehicle control will be done in the ANCOVA model. Two-sided 90% confidence intervals for the difference of each OTT166 dose group minus combined vehicle control will be calculated. Additional details on

sensitivity analyses and missing data imputation of the secondary endpoints will be provided in the SAP.

Analyses of exploratory imaging outcome measures will be described in the SAP.

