
treatment is superior to vehicle control using a 1-sided alpha of 0.05, provided that the true treatment effect (active treatment efficacy rate minus vehicle control efficacy rate) is at least 0.20 and the vehicle control efficacy rate is at most 0.06.
 
The two OTT166 dose regimens will cover a 2-fold dose range in total daily dose (5.0 mg/day to 10.0 mg/day).
	

Population:
 
The population will be participants with Type 1 or Type 2 diabetes under adequate control as evidenced by glycosylated hemoglobin (HbA1c) less than or equal to 12.0% , who show typical fundus alterations, and diagnosed with moderately severe to severe NPDR or mild PDR, as defined by the DRSS Steps 47, 53, and 61B, with the PDR population capped at no more than 20% of all randomized participants. Baseline Best-Corrected Visual Acuity (BCVA) must be \geq 69 Early Treatment Diabetic Retinopathy Study (ETDRS) letters (Snellen equivalent 20/40) and central subfield thickness (CST) must be \leq 325 μm at the screening and baseline examinations. DRSS steps, CST measurements and the presence of a normal foveal contour must be confirmed by the central reading center.
	
Primary Objectives:	Primary Endpoints:
To characterize the safety of topical OTT166 in participants with DR	
 Proportion of participants who develop treatment-emergent adverse events (TEAEs) through Week 24
To characterize the efficacy of topical OTT166 in participants with DR	
 Proportion of participants who have improved by \geq 2 steps from baseline at Week 24 as determined by central reading center assessment using the DRSS
Secondary Objectives:	Secondary Endpoints:
To determine if topical OTT166 will prevent or delay the occurrence of visually threatening complications (VTC), defined as PDR worse than mild and/or anterior segment neovascularization (ASNV) and/or CI-DME (defined below)	
 Proportion of participants developing worse than mild PDR (DRSS 65 and above) at Week 24 Proportion of participants who develop ASNV determined by the investigator at Week 24 Time to development of PDR worse than mild (DRSS 65 and above) Proportion of participants who develop CI-DME at Week 24
To determine if topical OTT166 will prevent or delay the occurrence of CI-DME. (CI-DME	
 Time to development of CI-DME

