2.15.1 Schedule of Activities

Table 1 OTT166 201 Phase 2 DR Study: Schedule of Activities (Through Week 24 – Primary Endpoint)

Study Procedure	Screening Visit 1	Baseline (BL) Visit 2	Visit 3	Visit 4	Visit 5	Visit 6	Visit 7	Visit 8 ^a
Week	--	0	4	8	12	16	20	24
Day (visit window)	-21 to -1	1	29 ± 7 days	57 ± 7 days	85 ± 7 days	113 ± 7 days	141 ± 7 days	169 ± 7 days
Screening/Baseline (BL):								
Informed consent	X							
Inclusion/exclusion	X	X						
Medical and ophthalmic history	X							
Demographics	X							
Randomization		X						
Interval Medical Review:								
Review of concomitant medications	X	X	X	X	X	X	X	X
Continue study treatment ^b		X	X	X	X	X	X	
Ocular Assessmentsⁿ:								
Refraction and BCVA (ETDRS)	OU	OU	OU	OU	OU	OU	OU	OU
Slit lamp examination	OU	OU	OU	OU	OU	OU	OU	OU
Assessment of cornea ^c	OU	OU	OU	OU	OU	OU	OU	OU
Intraocular pressure ^d	OU	OU	OU	OU	OU	OU	OU	OU
Indirect ophthalmoscopy	OU	OU	OU	OU	OU	OU	OU	OU
4-wide or 7-field color fundus photography (mandatory) ^e	OU	OU	SE	SE	OU	SE	SE	OU
SD-OCT (widerfield if available)	OU	OU	SE	SE	OU	SE	SE	OU
OCTA (if available)	OU							OU
Wide field Fluorescein Angiography ^m	OU							OU
Gonioscopy	OU							OU

Study Procedure	Screening Visit 1	Baseline (BL) Visit 2	Visit 3	Visit 4	Visit 5	Visit 6	Visit 7	Visit 8 ^a
Week	--	0	4	8	12	16	20	24
Day (visit window)	-21 to -1	1	29 ± 7 days	57 ± 7 days	85 ± 7 days	113 ± 7 days	141 ± 7 days	169 ± 7 days
Non-Ocular Assessments:								
Physical examination ^f	X							
Vital signs ^g	X	X	X	X	X	X	X	X
Adverse events ^h	X	X	X	X	X	X	X	X
IP adherence review ^o			X	X	X	X	X	X
Laboratory Testing:ⁱ								
Hematology, blood chemistry, urinalysis, and HbA1c ^{j,l}	X							X
Pregnancy test, women of childbearing potential ^k	serum	urine	urine	urine	urine	urine	urine	urine

Abbreviations: BCVA: best corrected visual acuity; BL: baseline; ETDRS: Early Treatment Diabetic Retinopathy Study; HbA1c: glycosylated hemoglobin; OCTA: optical coherence tomography – angiography; OU: both eyes; SD-OCT: spectral-domain optical coherence tomography; SE: study eye.

- ^a Participants who are withdrawn from the study before Week 24/Visit 8 will be asked to return to the clinic to complete the end of study assessments.
- ^b Participants will continue to receive study treatment based on exam findings, AE review, and verification that rescue criteria are not met.

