2.16.5 Optical Coherence Tomography (OCT)

Structural OCT (widefield preferred) will be performed by using spectral domain devices. The specific device models accepted for the study will be defined by the central reading center. OCTs will be performed at every visit by qualified technicians following an acquisition protocol of the central reading center. OCTs will also be used for local safety assessment. Newly found clinically significant pathologies should be reported as AEs. All obtained images will be sent to the central reading center for evaluation, and central reading center data will be used for the final analysis.

At screening, a standardized set of OCT images will be sent to the central reading center for evaluation and eligibility assessment. Beside central subfield thickness within the central 1 mm (CST) and whole macular volume also the presence of center involving and non-center involving macular edema will be assessed. SD-OCT will be also assessed for foveal contour and several exploratory outcome parameters and morphologic predictive biomarkers.

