### 4.2 General Presentation Considerations

‘Baseline’ is defined as the last available pre-treatment assessment for safety assessments. For DRSS score, the Baseline value is defined as the Screening/Visit 1 result. Pre-treatment values for DRSS were collected at the Screening/Visit 1 using fluorescein angiography in addition to fundus photography whereas Baseline/Visit 2 used fundus photography only. Participants were enrolled into the study and randomized to the study treatment based on the Screening/Visit 1 DRSS result. All other efficacy analyses that do not use DRSS score will use the last available pre-treatment assessment as Baseline. If an assessment is taken on the same day as first administration of study drug, it is eligible to be used as the Baseline value. This is considered acceptable as this measurement is still the best representation of the Baseline value of the given assessment since it is highly unlikely that the study drug could have an impact on any measurement in a short period of time.

‘End of Study’ is defined as the last available post-treatment assessment.

‘Study Day’ will be calculated relative to the date of randomization for untreated randomized participants and relative to the date of first dose for treated participants. If event is prior to the first dose, then study day is calculated as:

$$\text{Date of Event} - \text{Date of Day 1.}$$

If event is after the first dose, then study day is calculated as:

$$\text{Date of Event} - \text{Date of Day 1} + 1.$$

‘Study day 1’ is defined as the date of randomization for untreated randomized participants or the date of first dose for treated participants.

Time to event analyses will be calculated from Study Day 1, including time to DRSS-related endpoints comparing to the Baseline value. These analyses will consider only post-Baseline assessments. The Visit 2/Baseline visit will not be considered.

Duration of Treatment (days) will be calculated as:

$$\text{Last Date of Dose} - \text{First Date of Dose} + 1.$$

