The time to event secondary endpoints will be defined as time to first development of an event and will be estimated based on the Kaplan-Meier method, along with a 90% confidence interval. Analyses will be based on observed data, where participants who receive rescue medication will be censored at the start of rescue medication. A stratified log-rank test adjusting for the randomization stratification factor will be performed, to compare the combined vehicle control with each treatment group. Additionally, a stratified Cox proportional hazards model adjusting for the randomization stratification factor will be employed to estimate the hazards ratio between the combined vehicle control and each treatment group.

Continuous secondary endpoints involving change from BL to Week 24 will be analyzed using an analysis of covariance (ANCOVA) model with BL measurement of the variable as a covariate and treatment group and the randomization stratification factor as fixed factors. As a sensitivity analysis of the continuous secondary endpoints involving change from BL to Week 24, a rank-based ANCOVA model will be employed. The pair-wise comparisons of each OTT166 dose group versus combined vehicle control will be done in the ANCOVA model. Two-sided 90% confidence intervals for the difference of each OTT166 dose group minus combined vehicle control will be calculated.

The specific reasons for meeting rescue criteria as described in protocol section 2.14.9 will also be summarized using number and percentage by treatment group.

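### The ANCOVA for change in BCVA and CST adjusts for only one of two scheduled pre-dose readings, leaving some already-collected precision unused

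*Protocol*

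**What the plan says.** - **Model.** Protocol 2.21.2.2 specifies one pre-dose covariate for continuous secondary endpoints: an ANCOVA "with BL measurement of the variable as a covariate and treatment group" and stratum as factors. SAP 4.10.3 has the same "model with BL measurement of the variable as a covariate and treatment group and the randomization stratification factor as fixed factors".
- **Baseline.** Protocol 2.21.1: "The BL value for analysis and reporting will be based on the last (non-missing) measurement before dosing on Day 1". SAP 4.2 agrees for BCVA and CST: "All other efficacy analyses that do not use DRSS score will use the last available pre-treatment assessment as Baseline". It adds that for a reading taken on the day of first dose, "it is eligible to be used as the Baseline value".
- **Imputation.** SAP 4.10.1.2 imputes missing Week 24 BCVA and CST from treatment group, stratum and the single baseline score. Where the composite strategy applies, it substitutes the worst value observed among all participants.
- **Schedule.** Table 1 (Protocol 2.15.1) lists BCVA and SD-OCT in both eyes at Visit 1 (Day -21 to -1) and Visit 2 (Day 1). Protocol 2.16.5 confirms that "OCTs will be performed at every visit by qualified technicians".
- **Eligibility.** The Synopsis sets the BCVA floor of 69 letters and the CST ceiling of 325 µm in one sentence that ends "at the screening and baseline examinations". The closing phrase could be read as applying to CST alone, but Table 1 schedules both measurements at both visits.

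Neither document enters the Visit 1 BCVA or CST value as a covariate, averages it with Visit 2, or gives an SD or between-visit correlation for either variable.

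**The concern.** One reading carries visit-to-visit measurement error, so it predicts the Week 24 value less well than two readings taken a few weeks apart. Visit 1 precedes randomization, so adjusting for it cannot bias the randomized comparison. It also leaves the endpoint, the estimand and the definition of change as they are.

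Change in BCVA and change in CST serve two separate secondary objectives, with about 70 participants per comparison group and no stated power. The stake is the width of the 90% intervals for these two endpoints.

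**Working it through.** **1. The plan's own figure.** The only sizing figure is for the primary binary endpoint: 0.06 v 0.26, one-sided 0.05, 90% power, continuity-corrected chi-square (Protocol 2.20.1).

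- Uncorrected n = [1.645·√(2·0.16·0.84) + 1.282·√(0.06·0.94 + 0.26·0.74)]² / 0.20² = 55.7, so 56.
- Corrected n = (55.7/4)·[1 + √(1 + 4/(55.7·0.20))]² = 65.3, so 66 per group. Power at 66 is 90.3%.
- Enrolment: 66/0.95 = 69.5, so 70.

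The figure reproduces. It says nothing about BCVA or CST.

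**2. Formula for the gain.** Let ρ2 and ρ1 be the correlations of the Visit 2 and Visit 1 readings with Week 24, and r the correlation between the two readings. With the Visit 2 value already a covariate, modelling change leaves the same residual as modelling the Week 24 value. Adding Visit 1 lowers residual variance by the fraction

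(ρ1 − ρ2·r)² / [(1 − ρ2²)(1 − r²)].

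If ρ1 = ρ2 = ρ, this becomes ρ²(1 − r) / [(1 + r)(1 − ρ²)].

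**3. Equally predictive readings** (correlations assumed).

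| ρ | r | Calculation | Fall in residual variance |
|---|---|---|---|
| 0.7 | 0.80 | 0.49·0.20 / (1.80·0.51) | 10.7% |
| 0.7 | 0.85 | 0.49·0.15 / (1.85·0.51) | 7.8% |
| 0.7 | 0.90 | 0.49·0.10 / (1.90·0.51) | 5.1% |
| 0.7 | 0.95 | 0.49·0.05 / (1.95·0.51) | 2.5% |
| 0.5 | 0.95 | 0.25·0.05 / (1.95·0.75) | 0.9% |
| 0.8 | 0.80 | 0.64·0.20 / (1.80·0.36) | 19.8% |

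**4. Visit 1 slightly less predictive** (ρ2 = 0.7).

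- ρ1 = 0.65, r = 0.80: (0.65 − 0.56)² / (0.51·0.36) = 4.4%.
- ρ1 = 0.67, r = 0.90: (0.67 − 0.63)² / (0.51·0.19) = 1.7%.
- ρ1 = 0.63, r = 0.90: zero.

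**5. Worst-value substitution.** Substituted outcomes add variance that no baseline reading explains. Large-sample simulation used ρ = 0.7, a worst value assumed at −3 SD, and replacement at random.

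| Replaced | r = 0.80 | r = 0.90 |
|---|---|---|
| None | 10.8% | 5.1% |
| 5% | 5.2% | 2.5% |
| 10% | 3.4% | 1.5% |

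Truncating both baselines at −1 SD as well gives 9.0% and 4.6% with none replaced, 4.1% and 2.1% at 5%, and 2.5% and 1.3% at 10%.

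**6. Simulation at trial size, BCVA only.** Settings: 70 v 70, 1,500 trials per scenario, between-participant SD 5-6 letters, visit error SD 2-4, true-change SD 3-5, mean 78 or 80, entry at 69 or more at both visits, effect 2 letters; all but the group size and entry floor are assumed.

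- No substitution: residual variance ratios of about 0.89-0.95.
- 5% replaced: 0.93-0.97.
- 10% replaced: 0.95-0.98.

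So the fall with 5-10% replaced is about 2-7%.

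**7. What this buys.** The interval narrows by 1 − √(1 − g), where g is the fall. Starting from 80% power, one-sided 0.05, new power is Φ(2.486/√(1 − g) − 1.645).

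- g = 5-11%: interval 2.5-5.7% narrower; power 81.8-83.9%.
- g = 2-7%: interval 1.0-3.6% narrower; power 80.7-82.5%.

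**8. Cost.** With 210 participants and six fitted parameters (intercept, two treatment, two stratum, one slope), 204 residual degrees of freedom become 203. If the added covariate were useless, variance would rise by roughly 204/203 − 1 = 0.5%.

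**The case against.** The strongest reply is that nothing is wrong. ANCOVA on the last pre-dose value is valid, pre-specified and consistent between Protocol and SAP, and the endpoints are secondary in a trial with no multiplicity adjustment. This stands: the point is an efficiency improvement, not a correction.

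The second reply is that Visit 1 may be the poorer reading. It can be 21 days old, or older where Protocol 2.12 allows screening to extend to six weeks. Contact lens wearers stop at screening and have a 14-day stabilization period before baseline (Protocol 2.14.8), so their Visit 1 BCVA may be less comparable. This lowers the gain, as step 4 shows, but does not defeat the change. With its own coefficient, a weak Visit 1 reading simply receives little weight. It is a reason to enter the two readings separately and not to average them.

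The third reply is that rescue in the study eye is a composite event in the primary estimand (SAP 3.2.2). If that mapping carries over to BCVA and CST, substituted values dilute the gain. This stands and is why the 2-7% range is given. In the trial-size runs with mean 80, power rose by about 0.7-2.4 points with 5% replaced and 0.2-1.4 points with 10%, the latter close to simulation noise.

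**Conclusion.** Two pre-dose readings of BCVA and CST are scheduled for every participant, and the ANCOVA and its imputation model use one. The loss is real but modest, and conditional. Residual variance would fall about 5-11% at ρ = 0.7 and r = 0.8-0.9, about 1-20% for ρ of 0.5-0.8 and r of 0.80-0.95, and about 2-7% with 5-10% worst-value substitution. It would be lower still if Visit 1 predicts Week 24 less well.

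Three stronger readings are tempting and not supported:

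- **That 5-11% is a figure for this trial.** The documents give no correlation or SD from which to derive it. The same caution applies to converting it into sample size: 140/0.95 − 140 = 7 and 140/0.89 − 140 = 17 extra participants per 140. At 2-7% the equivalent is about 3 to 11 (140/0.98 − 140 = 2.9; 140/0.93 − 140 = 10.5).
- **That it applies equally to OCT.** CST was not simulated. If CST is highly repeatable, the gain may sit near the low end, such as 2.5% at r = 0.95 with ρ = 0.7.
- **That the planned analysis is flawed.** It is unbiased as written, and neither the primary endpoint nor the sample size is touched.

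**What to change.** In SAP 4.10.3, keep Baseline as the last pre-dose value for computing change, and add the Visit 1 value of the same variable as a second, separate covariate in the BCVA and CST ANCOVA. Make the same addition to their Week 24 imputation model in SAP 4.10.1.2, so that the two models agree. State what happens if Visit 2 is missing: Baseline then falls back to Visit 1 and the two covariates coincide for that participant.

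SAP 4.14 gives the SAP precedence over the Protocol's planned analyses and allows changes before database lock, so a SAP edit is enough; Protocol 2.21.2.2 can be aligned if it is next amended. Make the change before unmasking, because a covariate added later would look data-driven. It needs no new visit, procedure or data, and costs one degree of freedom.
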